## 8.3.6. Adverse Events of Special Interest

Adverse events of special interest (AESI) are defined as transfusion reactions as specified in Appendix 4, and will be registered in the Norwegian Directorate of Health's system for Hemovigilance monitoring.

## 8.4. Biomarkers and immunological assessments

Collection of biological samples for research is also part of this study. Samples will be collected in the general COVID-19 (SARS-CoV-2) Biobank at Oslo university hospital (REK:135924). The following samples for biomarker research will be collected from all participants in this study as specified in the SoA and Appendix 2:

- Oropharynx samples will be tested for presence of SARS-CoV-2 RNA to evaluate their association with the observed clinical responses to convalescent plasma.
- Blood samples will be tested for hemoglobin, thrombocytes, leukocytes with differential count and CRP. These samples will be tested by the sponsor or sponsor's designee.
- Serum samples will be tested for antibodies to SARS-CoV-2 Spike protein. These samples will be tested by the sponsor or sponsor's designee. Other analyses may be performed to further characterize the antibody profile after transfusion.
- Other samples may be used for research to develop methods, assays, prognostics and/or companion diagnostics related to SARS-CoV-2, pathogenesis and protection mechanisms.
- Samples may be stored for a maximum of 5 years following the last participant's last visit for the study at a facility selected by the sponsor to enable further analysis of immune responses to coronaviruses.

## 9. Statistical Considerations

## 9.1. Statistical Hypotheses

This study is designed to detect a 40% reduction in mortality with treatment of COVID-19 with convalescent plasma among the study population, under the assumption that the mortality in the standard care group is 30%.

The primary null hypothesis is that there is no difference in mortality between standard care and standard care + treatment with convalescent plasma.

The primary alternative hypothesis is that there is a difference in mortality between standard care and standard + treatment with convalescent plasma.

# 9.2. Sample Size Determination

In countries with at least 100 deaths in total and data are available, the proportion of COVIDrelated deaths among care home residents ranged from 19% in Hungary to 62% in Canada; for Norway this was 61%.

The case fatality rate among COVID-19 patients in institutions outside hospitals is inconsistently reported across multiple Western countries, including Norway (https://ltcCOVID.org).

In a study from Wuhan, China with 201 COVID-19 patients the CFR was 21.9% among a population with median age 51 years (IQR 43-60)(Wu et al 2020). Others have reported CFR among COVID-19 patients aged 80 years or above in Hubei, China at 39.0% (95% KI: 31.1-48.9%) and at 89.0% (95% KI: 56.2-99.6%) in North Italy (Hauser et al 2020)

Estimates for reduction in mortality among patients receiving convalescent plasma for treatment of COVID-19 have not been found. We therefore consider several different scenarios below (Table 1 and 2).

The sample size-calculations are based on a primary outcome of time to death, to be analyzed by a Cox regression model.

We consider this to be the most realistic scenario:: To achieve 80% power to detect a difference between 30% mortality in the standard care group and 18% mortality in the convalescent plasma group (a relative reduction in mortality of 40%, which corresponds to a hazard ratio of approximately 0.60), N = 502 patients need to be recruited and 121 deaths need to be observed during the follow-up period.

There will be one interim analysis of efficacy (on the primary outcome) after half the patients have completed the first 28 days of follow-up. We will use a O'Brien and Fleming group sequential design (Wassmer&Brannath, 2016), where the interim analysis will be performed with a significance level of  $\alpha$ =0.0052, and the final analysis (after all patients have completed the

study) will be performed with a significance level of  $\alpha$ =0.048, thus maintaining an overall significance level of 5%. The inflation factor with this design is 1.008, raising the total number of patients to N = 502\*1.008 = 506. The interim analysis will be carried out on 253 patients.

	Relative reduction of mortality in the convalescent plasma group					
Mortality in the standard care group	20% #events = 631	30% #events=247	40% #events=121	50% #events=66		
20%	N = 3503	N = 1452	N = 752	N = 436		
30%	N = 2336	N = 968	N = 502	N = 291		
40%	N = 1752	N = 726	N = 376	N = 218		
50%	N = 1402	N = 581	N = 301	N = 175		

 Table 1: Sample size (and number of events) to achieve 80% power with a 5% significance level

Table 2: Corresponding mortality rates in the convalescent plasma group

	Relative reduction of mortality in the convalescent plasma group			
Mortality in the standard care group	20%	30%	40%	50%
20%	16%	14%	12%	10%
30%	24%	21%	18%	15%
40%	32%	28%	24%	20%
50%	40%	35%	30%	25%

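### Section 9.2 uses the ratio of 28-day mortalities (18%/30% = 0.60) as the hazard ratio, so the stated deaths, N and 80% power do not belong to 30% versus 18%, nor to any mortality pair in Table 1

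*Protocol*

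**What the plan says.** Section 9.1 states that the study is "designed to detect a 40% reduction in mortality", with 30% mortality assumed under standard care. Section 9.2 names the method: "The sample size-calculations are based on a primary outcome of time to death, to be analyzed by a Cox regression model". It then fixes the main scenario: "To achieve 80% power to detect a difference between 30% mortality in the standard care group and 18% mortality in the convalescent plasma group", glossed as "a relative reduction in mortality of 40%, which corresponds to a hazard ratio of approximately 0.60". For this it gives 121 deaths and N = 502, raised to 506 by the factor 1.008 for one O'Brien-Fleming interim analysis (levels 0.0052 and 0.048).

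Table 1 ("Sample size (and number of events) to achieve 80% power with a 5% significance level") extends the calculation to control mortalities of 20% to 50% and relative reductions of 20% to 50%. Each column carries a single event count (631, 247, 121 and 66) for all four control mortalities. Table 2 lists the plasma-arm mortality for each cell, always as control mortality times one minus the reduction. The columns are therefore ratios of cumulative mortality.

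**The concern.** A ratio of cumulative risks and a hazard ratio differ unless events are rare. At 30% mortality they are visibly apart, and the gap widens as control mortality rises. The face of Table 1 shows the problem: a fixed relative reduction in mortality corresponds to a different hazard ratio at each control mortality, so the required number of deaths cannot be constant down a column.

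At stake is whether the design's headline claim is true. The scenario in question is the one the protocol calls most realistic, and it sets N = 506 and the 253-patient interim. Table 1 is also the only guide in the document to what other mortality levels would require, and section 9.2 itself says that fatality in these institutions is inconsistently reported.

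**Working it through.** **Inputs.** Overall level 5% (Table 1 caption), taken as two-sided because the alternative in section 9.1 is a difference; power 80%; 1:1 allocation (section 9.3.1); mortality 30% and 18% (sections 9.1 and 9.2); 28-day follow-up for all patients (section 3). No dropout rate is given for the calculation, so none is used.

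**Step 1: reproduce the plan.** Schoenfeld's formula for 1:1 allocation is D = 4(z₀.₉₇₅ + z₀.₈₀)² / (ln HR)², with 4(1.960 + 0.8416)² = 31.40.

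- HR = 0.60: D = 31.40 / 0.2609 = 120.3, rounded up to 121.
- N = 120.3 / mean mortality = 120.3 / 0.24, rounded up to 502.

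Setting HR = 1 − relative reduction in this way reproduces all 4 event counts and all 16 values of N in Table 1 exactly. Alternatives do not: Freedman's formula gives 126 deaths and N = 525, and a one-sided test gives 95 deaths.

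**Step 2: the hazard ratio that the mortalities imply.** Under proportional hazards, 1 − p₁ = (1 − p₀)^HR, so HR = ln(1 − p₁) / ln(1 − p₀).

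- 30% versus 18%: HR = ln(0.82) / ln(0.70) = 0.1985 / 0.3567 = 0.556.
- D = 31.40 / 0.3437 = 91.3, rounded up to 92.
- N = 91.3 / 0.24, rounded up to 381 (385 after multiplying by 1.008).
- Stated over required N: 502 / 381 = 1.32.

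**Step 3: power at the planned size.**

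- 121 deaths, no interim: Φ(√121 × 0.5863 / 2 − 1.960) = Φ(1.265) = 89.7%.
- N = 506 (506 × 0.24 = 121.4 expected deaths) with the two-look design at 0.0052 and 0.048: 89.6% for HR 0.556 and 80.1% for HR 0.60.
- Simulated log-rank test with exponential survival censored at 28 days, N = 502: 88.8%.

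**Step 4: a check without a hazard ratio.** A two-sided comparison of 30% with 18% as proportions needs N = 396 for 80% power, and has 88.5% power at 502 and 88.7% at 506. The overstatement therefore does not come from the proportional-hazards conversion.

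**Step 5: reading it the other way.** HR 0.60 with 30% control mortality means plasma mortality 1 − 0.70^0.60 = 19.3%, a relative reduction of 1 − 19.3/30 = 36%. N is then 120.3 / 0.2463, rounded up to 489.

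**Step 6: Table 1 recomputed.** Each cell shows implied HR; deaths; N, with the stated N in brackets.

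| Control mortality | 20% reduction | 30% reduction | 40% reduction | 50% reduction |
|---|---|---|---|---|
| 20% | 0.781; 516; 2866 (3503) | 0.676; 205; 1204 (1452) | 0.573; 102; 633 (752) | 0.472; 56; 372 (436) |
| 30% | 0.769; 458; 1693 (2336) | 0.661; 184; 718 (968) | 0.556; 92; 381 (502) | 0.456; 51; 226 (291) |
| 40% | 0.755; 398; 1104 (1752) | 0.643; 162; 474 (726) | 0.537; 82; 255 (376) | 0.437; 46; 153 (218) |
| 50% | 0.737; 338; 749 (1402) | 0.621; 139; 327 (581) | 0.515; 72; 178 (301) | 0.415; 41; 109 (175) |

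The excess runs from 17% (436/372) to 87% (1402/749). Power at the stated event counts runs from 86% to 97%.

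**The case against.** The strongest reply is that the hazard ratio is the parameter the Cox model tests, so it is the hazard ratio that should be kept. The counts 631, 247, 121 and 66 are correct for hazard ratios of 0.80, 0.70, 0.60 and 0.50, and a constant count down each column is then right. The stated N would be only about 1% to 6% too large (502 against 489 in the main scenario). This is true of the event counts, but it is not the target the protocol sets. Section 9.1, the column heading of Table 1 and the whole of Table 2 define the effect as a reduction in cumulative mortality. On this reading the detectable plasma mortality would be 19.3%, not 18%.

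A second reply is that the error is conservative and leaves the conduct of the trial alone. That stands. The type I error, the two significance levels, the inflation factor and the patient-count trigger for the interim do not depend on the assumed hazard ratio. The extra patients may also be useful. As an illustration only, since the protocol gives no such rate: if 10% of the plasma arm had control-group mortality, plasma mortality would be 0.9 × 18% + 0.1 × 30% = 19.2%, and power at 506 would be roughly 81 to 82%. But the protocol declares no such allowance, so the excess cannot be read as a planned margin.

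Third, the text says the hazard ratio is only approximate. Required deaths vary with 1/(ln HR)², so moving from 0.60 to 0.556 takes them from 121 to 92. Table 1 also applies the substitution exactly in every cell, including 50% control mortality with a 20% reduction, where 0.80 stands in for 0.737.

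**Conclusion.** The concern holds. The hazard ratio of 0.60 and the mortality pair 30% and 18% do not correspond, and 121 deaths and N = 502 give 80% power for the former only. For the stated scenario 80% power needs 92 deaths and N = 381, and the planned 506 patients give about 89 to 90%. Every cell of Table 1 has the same fault with respect to its labelled mortality reduction.

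These figures assume proportional hazards, complete 28-day follow-up and full delivery of the assigned treatment. The direction of the error is conservative: nothing here suggests that the trial is too small for the effect it names. The fault is that the power, event count and N as written are not those of the design as described.

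**What to change.** Keep N = 506 and make the statement true in one of two ways:

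- keep the target of 30% versus 18%, give the hazard ratio as 0.56, and state about 89 to 90% power; or
- keep 121 deaths and 80% power, and give the target as a hazard ratio of 0.60, that is 30% versus 19.3% mortality, a 36% relative reduction.

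Use the chosen target in section 9.1 as well. Recompute Table 1 with HR = ln(1 − p₁)/ln(1 − p₀), so that deaths vary by row as well as by column, and state the conversion and its proportional-hazards assumption under the table. If part of the surplus is meant to cover dropout or incomplete treatment, say so and give the assumed rates.

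The cost is a few sentences and one table. No patients are added, and the test and the stopping levels are unchanged.

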## 2.2. Background

Originating in Wuhan Province of China in late 2019, a new coronavirus named SARS-CoV-2 has spread throughout much of the world. The virus, which causes respiratory infection and in some a serious respiratory illness, was declared a pandemic by WHO in March. As of ultimo May 2020, the number of detected infected is approaching 5,5 million worldwide, and more than 350,000 people have died. In addition, the numbers of actual infected are underestimated as adequate testing in large parts of the world is impossible and a substantial number of cases are

asymptomatic. In Norway, drastic measures have achieved a controlled spread of virus, and we are currently able to treat the number of patients within the total hospital care capacity, including intensive care units. However, it must be assumed that the spread of infection will continue and that a significant number of patients will die before vaccines become available. Although most people experience mild infection, serious illness and high mortality has been observed especially among the elderly, individuals with comorbidities such as cardiovascular disease, diabetes and obesity.

As per end of May 2020, about 90% of the 235 deaths reported in Norway due to COVID-19 had occurred between patients aged 70 years or more, and 60% of all deaths occurred among patients admitted to institutions outside hospitals. Within outbreaks in care homes in Norway, case fatality rates of 15 to 50% have been reported in 2020. Patients in care homes are not prioritized for any advanced supportive medical treatment for COVID-19, and mechanical ventilation is not an option in these institutions.

The WHO has provided strategic guidelines (WHO Roadmap) for prioritization of which treatment alternatives should be systematically tested, and included convalescence plasma an alternative to consider. Norwegian hospitals are already part of the WHO Solidarity treatment trial to evaluate the safety and efficacy of antiviral treatments. Based on the potential to provide an effective COVID-19 treatment with reliably local supply until a safe and effective vaccine is available, Norwegian blood banks led by the Norwegian Health Directorate have converged on a national project for the collection and testing of convalescence plasma.

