# 9.5. Interim Analyses

The DMC will perform an interim analysis of effect after half of the patients (n=253) have completed the first 28 days of follow-up and data on mortality are available for all these patients. The efficacy analysis will be performed on the primary outcome with a significance level of  $\alpha$ =0.0052 (see Section 9.2). If the analysis demonstrates an effect of the intervention, the study will be stopped early. Details will be presented in the DMC charter.

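### The final level of 0.048 is fixed whatever share of the deaths has occurred at the interim, so the overall 5% is exact only at the planned one half (minor)

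*Protocol*

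**What the plan says.** All references are to the protocol.

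- **Test.** Section 9.2: "The sample size-calculations are based on a primary outcome of time to death, to be analyzed by a Cox regression model". The same section requires 121 deaths and 502 patients for 80% power at 30% versus 18% mortality, a hazard ratio of about 0.60.
- **Design.** Section 9.2: "We will use a O'Brien and Fleming group sequential design", with 0.0052 at the interim and 0.048 at the final analysis. An inflation factor of 1.008 raises the total to 506. The result is described as "thus maintaining an overall significance level of 5" per cent.
- **Timing.** Section 9.2: "There will be one interim analysis of efficacy (on the primary outcome) after half the patients have completed the first 28 days of follow-up", and then "The interim analysis will be carried out on 253 patients". Section 9.5 repeats it: "The DMC will perform an interim analysis of effect after half of the patients (n=253) have completed the first 28 days of follow-up". It adds that mortality data must be available for all of them and leaves details to the DMC charter.

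Neither section gives a number of deaths for the interim, a spending function, or a rule that adapts the final level to the deaths actually seen.

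**The concern.** A two-look boundary controls the overall error through the correlation between the interim and final test statistics. For a Cox or log-rank test this correlation is the square root of the death fraction t. Patients stand in for deaths only on average. The number of deaths among the first 253 patients varies by chance, and t also moves if mortality changes over the recruitment year or if recruitment ends below 506. Since 0.048 is fixed in advance, the overall error moves with t.

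At stake is the protocol's statement on its confirmatory error rate. In one direction the 5% is slightly exceeded. In the other, a little of it goes unused, which is most wasteful if recruitment stops before 253 patients: the interim as described does not take place, yet the text still sets the final test at 0.048.

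**Working it through.** **Inputs from the protocol.** Levels 0.0052 and 0.048; two-sided test (section 9.1 states the alternative as a difference); 253 and 506 patients; mortality 30% and 18%, 1:1, so 24% on average; hazard ratio 0.60; 80% power; inflation 1.008.

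**Step 1: reproduce the plan.**
- Deaths (Schoenfeld): 4 × (1.960 + 0.842)² / (ln 0.60)² = 120.3, rounded up to 121.
- Patients: 120.3 / 0.24 = 501.3, rounded up to 502; 502 × 1.008 = 506.
- Two-look O'Brien-Fleming constant at t = 0.5: c = 1.9774. The interim boundary is 1.9774 × √2 = 2.7965. The two-sided levels are 0.00517 and 0.04799, and the inflation factor is 1.0078.
- Expected deaths: 253 × 0.24 = 60.7 at the interim and 506 × 0.24 = 121.4 at the end, so the planned t is 0.5.

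All of the plan's figures reproduce.

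**Step 2: overall error with both levels held fixed.** Under the null hypothesis (Z₁, Z₂) is bivariate normal with correlation √t, and

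overall error = 1 − P(|Z₁| < 2.794 and |Z₂| < 1.977),

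where 2.794 and 1.977 are the two-sided critical values for 0.0052 and 0.048. The last column is the final level that gives exactly 5% when 0.0052 is kept at the interim.

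| t | Overall error with 0.0052/0.048 | Final level that gives 5% |
|---|---|---|
| 0.30 | 5.13% | 0.0467 |
| 0.40 | 5.07% | 0.0473 |
| 0.43 | 5.05% | 0.0475 |
| 0.50 | 5.00% | 0.0480 |
| 0.60 | 4.94% | 0.0486 |
| 0.70 | 4.88% | 0.0492 |

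As t approaches 0 the two statistics become independent, and the error tends to 1 − 0.9948 × 0.952 = 5.30%. That is the ceiling.

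**Step 3: which values of t to expect.**
- *Constant mortality, full recruitment.* The total is 121 × 1.008 ≈ 122 deaths. With 253 of 506 patients in the first half, the hypergeometric 95% range for first-half deaths is 52 to 70, so t runs from 0.43 to 0.57 and the error from 5.05% to 4.96%.
- *Changing mortality (assumed figures).* From 20% in the first half to 40% in the second: t = 0.20/0.60 = 0.33, error 5.11%. The reverse: t = 0.67, error 4.90%.
- *Recruitment ends at 300 (assumed), stable mortality.* t = 253/300 = 0.84, error about 4.8%.
- *Recruitment ends below 253.* There is no interim; a single test at 0.048 has an error of 4.8%.

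**The case against.** The case for leaving the text alone is substantial.

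- **The plan is coherent on its own assumptions.** Every patient in the interim has completed the fixed 28 days, so half of the patients means half of the expected deaths, and the 5% statement is right at that value. This stands.
- **The effect is tiny.** With constant mortality, chance moves the error by no more than about 0.05 percentage points. This stands, and it makes the point minor.
- **The DMC charter or the SAP may deal with it.** Neither is at hand. If the protocol had been silent on the final level, that would settle the matter. But section 9.2 itself fixes 0.048 and attaches the 5% statement to it without condition, so a different rule in another document would conflict with the protocol.

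Two stronger readings are tempting and do not hold. A reader might infer that 5% is kept only if exactly half of the deaths fall in the first 253 patients. It is not so: for t above 0.5 the error is below 5%, so the level is held, with a little to spare. A reader might also take the remark in section 2.2 that "case fatality rates of 15 to 50% have been reported in 2020" as evidence that mortality will drift over the trial. That range describes differences between care-home outbreaks. Each half of the trial would pool many homes, and nothing in the protocol predicts a rise over time, which is the direction that would push the error above 5%.

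**Conclusion.** The point holds as a small, cheap improvement. The pair 0.0052/0.048 gives 5% at the planned death fraction of one half, but section 9.2 states the 5% as if it did not depend on that fraction. The overall error is slightly too high if fewer than half of the deaths have occurred at the interim, and slightly conservative if more have, if recruitment falls short, or if no interim is held. The deviation is at most 0.3 percentage points upward and about 0.2 downward.

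This rests on the usual large-sample result that a Cox test accrues information in proportion to deaths, on a two-sided test, and on the interim and final analyses counting the same kind of death (within 28 days). The drift and shortfall scenarios are illustrations, not figures from the protocol. The sample size, the inflation factor and the interim level need no change.

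**What to change.** In sections 9.2 and 9.5, and in the DMC charter:

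1. Keep the interim at 253 patients with 28 days of follow-up, tested at 0.0052.
2. Replace the fixed 0.048 by the final level that gives 5% overall for the observed t, defined as primary-endpoint deaths in the interim analysis divided by those in the final analysis, both arms pooled, with correlation √t between the two statistics. Examples: 0.0473 at t = 0.40, 0.0480 at t = 0.50, 0.0492 at t = 0.70.
3. Use 0.05 at the final analysis if no interim was carried out.
4. Reword the 5% statement so that it refers to this rule, and give 0.048 as the value expected at t = 0.5.

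The cost is a sentence or two and no extra patients. The downside is that the final level is known only once the deaths have been counted, so the rule should be written down before the interim. Timing the look at 61 deaths instead is not needed: it would change how the trial is run, and since the final analysis is set by patients, it would not by itself secure t = 0.5.

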## 9.3. Statistical Analyses

A statistical analysis plan (SAP) will be finalized prior to database lock. The SAP will include detailed descriptions of the statistical analyses of the primary and all secondary endpoints. This section briefly describes the primary analysis and some general statistical methods and considerations..

